- At least one incident of contact sexual abuse between the ages 5-14 years;
- Current DSM-IV diagnostic criteria for MDD (as diagnosed with the use of the SCID);

Childhood Sexual Abuse/Resilient (CSA/RES):

- At least one incident of contact sexual abuse between the ages 5-14 years;
- Absence of past or current DSM diagnosis, including MDD or alcohol/substance abuse;

Non-traumatized, MDD (MDD):

- No incidents of childhood sexual, verbal, or physical abuse (ascertained using the Traumatic Antecedents Questionnaire);
- Current DSM-IV diagnostic criteria for MDD (as diagnosed with the use of SCID);

Non-traumatized, healthy controls (controls):

- No incidents of childhood sexual, verbal, or physical abuse (ascertained using the Traumatic Antecedents Questionnaire);
- Absence of any medical, neurological, and psychiatric illness (including alcohol/substance abuse)

Exclusion Criteria:

- Participants with suicidal ideation where study participation is deemed unsafe by the study clinician;
- Women who are not fully fluent (reading, speaking, & writing) in English;
- Pregnant women or women of childbearing potential who are not compliant with the requirements of a urine and blood pregnancy test. Pregnancy is determined by serum pregnancy tests conducted during sessions 1 and 4 and by a urine pregnancy test conducted during session 3.

- Women of childbearing potential not using adequate form of contraception. Adequate contraception includes birth control pills, birth control patch, birth control sponge, birth control vaginal ring, birth control shots, a non-metallic, MRI-compatible intrauterine device (IUD), condom, diaphragm, female condom, spermicide, partner with vasectomy, and abstinence. Those not of childbearing potential include post-menopausal for more than 6 months or surgically sterilized
- Failure to meet MRI or PET safety requirements.
- Serious or unstable medical illness, including cardiovascular, hepatic, renal, respiratory, endocrine (hypothyroidism), neurologic or hematologic disease;
- Past/current DSM diagnosis of: OCD, ADHD, schizophrenia, schizoaffective disorder, delusional disorder, bipolar disorder, mood congruent/incongruent psychotic features, substance dependence, substance abuse within the last 12 months (with the exception of cocaine or stimulant abuse, which will lead to automatic exclusion); Bulimia and Binge Eating Disorder within the last 2 years; Anorexia

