
concentrations of electrolytes, BUN, SGOT, SGPT, CPK, alkaline phosphatase, total bilirubin, albumin, total protein, blood pregnancy test, TSH, eGFR, and electrocardiogram (EKG), and a urine drug test. These tests must be performed within four weeks prior to amisulpride administration.

Preliminary screening for sex, handedness, neurological disorders, exclusionary physical conditions, medication status, weight, history of childhood trauma and history of depression, and MRI and PET safety will take place at the time of the initial telephone contact or interview or via the online screening survey on RedCap (a Partners secure website). Subjects will be re-screened for MRI safety at the beginning of the fMRI session.

To avoid the confounding effects of medication, only subjects off medication will be considered. Importantly, no subject will be requested to discontinue treatment for the purpose of participating in the studies proposed here. Further, if any subject becomes emergently ill or suicidal, access to emergency clinical care will be provided according to established procedures at McLean Hospital. If at any point between signing of consent and the conclusion of the second session, a subject becomes suicidal, homicidal, manic, or psychotic, (s)he will be withdrawn from the study and appropriate care and resources will be provided. Depending on the outcome of the first session, eligible participants will be assigned to one of four groups: (1) CSA between the ages of 5-14 with current diagnosis of MDD (*CSA/MDD*), (2) CSA between the ages of 5-14 without current or past diagnosis of Axis I or II disorders (*CSA/RES*), (3) current diagnosis of MDD without a history of CSA (*MDD*), and (4) healthy controls. Each group will contain 23 subjects who complete at least two imaging sessions (n=23/group).

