clinician or masters-level clinical interviewer (e.g., [name], M.Ed., LMHC) after a comprehensive psychiatric evaluation. The informed consent will clearly state that the subjects may quit participation at any time without penalty. Potential risks and benefits will be explained in full by the project staff, and the subjects will be asked to sign a consent form. The informed consent will be signed by the subjects and a licensed study clinician.

A subset of subjects ($n=20$) will be invited to participate in an additional component involving a skin biopsy immediately after they have completed the ERP session and will sign a separate informed consent form that will detail the risks of a small skin punch biopsy of their buttocks. The consent form will clearly state that participation is entirely voluntary and subjects may stop participation at any time, without a penalty or loss of benefits to which they are otherwise entitled. The procedure will be described in detail including a description of possible risks and benefits as well as steps taken to minimize the pain. Additionally, participants will be screened for ineligibility due to lidocaine allergy, skin adhesive (Dermabond) allergy, or history of or bleeding disorder. Consent will be acquired by [name], a physician board-certified in Internal Medicine, and the informed consent form will be signed by both [name] and the subjects.

Confidentiality of all subjects will be honored. Individual records will be made anonymous immediately after recording using numeric codes only accessible to the experimenters. Only the experimenters will have access to identifiable subject information, which will be stored in locked cabinets.

V. STUDY PROCEDURES

a. Study visits and parameters to be measured

This study will include four sessions (for a subset of participants ($n=20$; see details below), the ERP session will include a skin biopsy.)

Session 1 (SCID Session)

The first session will take place at the Center for Depression, Anxiety, and Stress Research or McLean Imaging Center at McLean Hospital (Director: [name]). The session will involve consenting, a clinical evaluation, and a medical assessment. The first session may be absolved in two separate visits if preferred by the participant (e.g. due to scheduling constraints). This will not affect data collection or reimbursement (participants will still be reimbursed at \$15/hour).

Consenting

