The Abnormal Involuntary Movement Scale (Guy, 1976) is a 12-item scale designed to record the occurrence of dyskinetic, involuntary movements. Participants will complete the AIMS task during the screening visit, prior to dismissal from the study and, in the case of a dystonic reaction during the scanning visit, during a final exit interview one to two weeks after the scanning visit.

Patients presenting with acute dystonic reaction, who are not in extreme distress, would be first treated with 50mg to 100mg of diphenhydramine orally. This is a safe and effective treatment, and widely available as an over-the-counter preparation. This is routinely used, (in oral or IV form), for example, for dystonic oculogyric crises in patients taking regular antipsychotic medication.

Patients with an acute dystonic reaction, who are in extreme distress would be directed to go to the nearest emergency room for treatment unless they were at McLean in which case IM cogentin or diphenhydramine would be given - after a brief assessment.

Benzotropine (1mg - 4mg orally or 1mg - 2mg IM/IV) (available only by prescription, or in a physician's office or the ER) is also safe and effective for resolving acute dystonic reactions. IM/IV cogentin or diphenhydramine tends to work faster than oral treatment - but both strategies are effective.

The AIMS task will be administered and scored by one of the study staff physicians (e.g., [name]., Ph.D.). During the AIMS task, participants are observed in stationary positions as well as during activated movements and any involuntary movements are recorded. This scale provides a quantitative measure of symptoms of dyskinesia and will help identify possible adverse reactions to the study drug, which are deemed unlikely due to the low and single dose administration.

Sessions 2-4 will include procedures for assessment of brain and cognitive functioning, specifically: a functional magnetic resonance imaging (fMRI) session, a positron emission tomography (PET) session, and an event related potential (ERP) session. The order in which these sessions are scheduled will depend on facility availability and convenience for participants.

ERP Session

This session will take place at the Center for Depression, Anxiety, and Stress Research at McLean Hospital (Director: [name]) and will be scheduled between 1 and 5pm to control for

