MRI data will be acquired on a 3T Siemens Tim Trio system using a 32-channel brain array coil. As in our prior work (Dillon et al 2009), data will be acquired using tilted slice acquisition (30° to the AC-PC line). To minimize susceptibility dephasing of spins and loss of magnetization, we will use a short echo time (30 ms), a GRAPPA acceleration factor of 2 to reduce the length of the EPI readout, and thin slices. During functional scans, gradient echo T2*-weighted echoplanar images will be acquired with: TR/TE: 3000/30ms; FOV: 224 mm; matrix: 64x64; 42 slices; in-plane resolution: 3.5 mm (2.5 mm slices, 1.0-mm gap); voxels 3.5 x 3.5 x 3.5 mm). The EPI acquisition will use prospective motion correction to minimize the effects of subject motion.

Self-report questionnaires will also be administered during the course of this session as well as the Columbia Suicide Severity Rating Scale (C-SSRS) to assess the emergence of suicidality. The appropriate procedures in the event of emergence of suicidality are outlined in ‘Psychosocial (non-medical) risks’ in section VII (Risks and Discomforts). In addition, urine drug and pregnancy tests will also be administered prior to the MRI scan.

In case that a subject is observed or determined to be in an altered state, (s)he will be evaluated by one of the study physicians (e.g., [name]., Ph.D.) and will be given appropriate care. Subjects deemed not to be at risk by one of the study physicians will be offered transportation by cab and reimbursed through a voucher. In the rare case that a subject exhibits dystonic symptoms, as assessed by AIMS, the subject will be invited back for a final exit interview one to two weeks after the scan at which time AIMS will be repeated.

Asymptomatic subjects will be dismissed 3 hours after administration of amisulpride, following a final evaluation by one of the study physicians (e.g., [name]., Ph.D.).

PET Session

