This session will take place at the Massachusetts General Hospital PET facility. After re-screening for compatibility with the PET environment, any remaining questions will be answered. Subjects will then be positioned in the gantry of a PET camera. Head alignment will be made, relative to the canthomeatal line, using projected laser lines. A Civco vac-lok cushion with velcro head strap will be used to prevent movement. A peripheral venous catheter will be inserted for radiopharmaceutical injection. 9 mCi of [¹¹C] altropane will be injected either by a physician or a trained nuclear medicine technicians and PET scanning will begin. The minimum specific activity that we use for C-11 altropane is 300 mCi / micromole at time of administration. PET data will be acquired using an ECAT EXACT HR + PET camera.

Subjects will be instructed that they are being continuously monitored and can be heard by the investigators if there is a problem. They will also be reminded that it is best for them to remain still

and refrain from any head, face or jaw movements. After conclusion of the PET scan, participants will be removed from the scanner.

Compared to other DAT tracers, altropane offers the following advantages (Fischman et al 2001; Madras et al 1998a,b,c): (1) rapid (max. accumulation 15-30 min post-injection) and specific striatal binding; (2) high selectivity for DA sites; (3) reversible binding kinetics; and (4) a relatively low level of nonspecific binding.

Prior to the PET scan, a blood serum pregnancy test and a urine drug will be administered, and participants will complete two tasks on cognitive functioning: the Optimism Bias Task, and the Self-Concept Attention Task.

Optimism Bias Task

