MID, PSST, PRTT, PRT, and Optimism Bias Tasks

Minimal discomfort may occur due to the time and effort related to completing these tasks.

Maastricht Acute Stress Test (MAST)

This paradigm is designed to induce physiological and psychological stress and thus most participants will find this task discomforting. However, participants are told that they can take their hand out of the ice water at any time if it is too uncomfortable. All subjects will be de-briefed at the end of the experiment regarding the stress manipulation.

e. Radiation risks

Exposure from the PET scan is considered small, and there is no evidence that it causes major health risks. Subjects will be exposed to approximately 2 milliSieverts (2 mSv). This amount of radiation is equal to about 55% of the annual background radiation everyone is exposed to each year from the earth and the sky. Subjects who have a history of cancer or a history of exposure to mutagens or radiation will be excluded from the study.

VIII. POTENTIAL BENEFITS

a. Potential benefits to participants

There will be no direct benefits to the subjects themselves for participating in this research.

b. Potential benefits to society

From a scientific perspective, the study may benefit people with depression and early life stress by furthering our understanding of the role of dopamine in the risk for and manifestation of depression and also the effects of early life stress on the dopaminergic system.

IX. MONITORING AND QUALITY ASSURANCE

a. Independent monitoring of source data

Not applicable.

b. Safety monitoring (e.g., Data Safety Monitoring Board, etc.)

As there is no clinical intervention, an external Data and Safety Monitoring Board will not be required. However, formal procedures for managing potential safety concerns will be implemented prior to study initiation.

Subjects are required to have a structural MRI scan of clinical quality at least once per year at McLean Hospital that is reviewed by a board certified radiologist or neurologist and a clinical report is generated usually within 2-4 days. If the subject has not received a structural clinical scan in the past year, one will be obtained for the present study during session 3 (fMRI session). Subjects will not receive more than one structural clinical MRI within a given 12-month period unless a follow-up scan is recommended by the radiologist who reads the scan.

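### The mandatory withdrawal rule for suicidal, homicidal, manic or psychotic subjects stops at session two of four, so the drug session, the stress-test session or both always fall outside it

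*Combined protocol and SAP*

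**What the plan says.** Section IV.a (Methods of enrollment) sets the rule. A subject who becomes suicidal, homicidal, manic or psychotic is withdrawn and given care if this happens "between signing of consent and the conclusion of the second session". No other section extends that window.

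Section V.a states: "This study will include four sessions". Session 1 is the SCID session. Sessions 2 to 4 are fMRI (with amisulpride or placebo), PET and ERP (with the Maastricht Acute Stress Test). On their order it says: "The order in which these sessions are scheduled will depend on facility availability and convenience for participants".

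Elsewhere the protocol does attach numbers to these sessions. Section IX.b says of a missing structural scan that "one will be obtained for the present study during session 3 (fMRI session". The exclusion criteria in Section III place "serum pregnancy tests conducted during sessions 1 and 4 and by a urine pregnancy test conducted during session 3". The PET Session text in Section V.a says: "Prior to the PET scan, a blood serum pregnancy test and a urine drug will be administered".

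Section IV.a also defines who counts toward the sample size: "Each group will contain 23 subjects who complete at least two imaging sessions".

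**The concern.** The rule is written as an obligation with a time limit, and the limit falls halfway through the study with no reason given. Elsewhere the protocol uses study-wide wording when it means it: the altered-state provision in Section IX.d applies throughout the study, and the urine drug test in Section III is repeated at every session. The cutoff in Section IV.a therefore reads as a real limit.

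Two of the four groups have current major depression and are off psychotropic medication. After the cutoff, such a subject may still face a dose of a D2/D3 antagonist, or a procedure designed to provoke physical and psychological stress that ends with the subject being told she performed poorly. Followed literally, the protocol does not require that a subject who becomes suicidal or psychotic after session two be withdrawn before those procedures. Two staff members could handle the same event differently and both be within the protocol.

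**Working it through.** This is a check of the text plus a count of orders. The plan states no figure that needs to be reproduced.

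**Step 1: reading by the protocol's own numbering.**
- fMRI is session 3. Section IX.b says so explicitly, and Section III agrees: its urine pregnancy test at session 3 matches the urine test before the MRI in Section V.a.
- PET is session 4. This is inferred: Section III puts serum pregnancy tests at sessions 1 and 4, and Section V.a puts a serum test at the SCID session and before PET.
- ERP is session 2, by elimination.

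On this reading the rule covers the SCID and ERP sessions. The drug session and the PET session (2 of 4) fall outside it.

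**Step 2: reading by calendar order.** Section V.a leaves the order of the three later sessions open, which gives 3! = 6 orders. The rule covers only whichever session comes second.

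| Session 2 | Session 3 | Session 4 | Drug session after cutoff | Stress test after cutoff |
|---|---|---|---|---|
| fMRI | PET | ERP | no | yes |
| fMRI | ERP | PET | no | yes |
| ERP | fMRI | PET | yes | no |
| ERP | PET | fMRI | yes | no |
| PET | fMRI | ERP | yes | yes |
| PET | ERP | fMRI | yes | yes |

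- Drug session after the cutoff: 4 of 6 orders.
- Stress test after the cutoff: 4 of 6.
- Exactly one of the two: 4 of 6. Both: 2 of 6. At least one: 6 of 6.

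These are counts of orders for a subject who attends all four sessions. They are not probabilities, because the documents do not say how often each order is used.

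**Step 3: who has sessions after the cutoff.** A subject counted toward the 23 per group completes at least two imaging sessions after the SCID session, so she attends at least one session numbered 3 or later. That applies to all 4 × 23 = 92 target completers, of whom 2 × 23 = 46 are in the two groups with current major depression.

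**Step 4: whether another provision fills the gap.**
- Section III: suicidal ideation excludes a subject if the study clinician judges participation unsafe. This is discretionary, and nothing says it is re-applied after enrollment. Bipolar and psychotic disorders are entry exclusions.
- Section IV.a: emergency care for any subject who becomes ill or suicidal. This is care, not withdrawal.
- Section V.a, fMRI Session: the "Columbia Suicide Severity Rating Scale (C-SSRS) to assess the emergence of suicidality", with a cross-reference to Section VII for what to do next.
- Section VII.d: at the EEG, fMRI, PET and biopsy sessions a physician is consulted and emergency services are called for imminent risk. Serious but not imminent risk is addressed only under the SCID session.
- Section V.b: a study physician at the imaging facility during the drug session.
- Section IX.d: physician evaluation and care for an altered state.

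None of these requires withdrawal after session two. None names homicidal, manic or psychotic states as a trigger. A positive suicidality rating on the dosing day leads to Section VII.d, which does not mention withdrawal.

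**The case against.** The strongest reply is that silence proves little. Section VII.d does not mention withdrawal at the SCID session either, where the Section IV.a rule plainly applies, so its silence about later sessions does not mean that subjects are kept in. Some exclusions, such as pregnancy and drug use, are tested again at later sessions. The suicidal-ideation criterion carries no stated time limit; read together with the suicidality scale at the fMRI session, it arguably lets a clinician stop a subject before dosing. An altered state could reasonably include mania or psychosis. Nothing prohibits withdrawal at any time, and a clinician would very probably stop a subject in acute crisis.

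Much of this stands. Later sessions are not without protection, and discretionary withdrawal remains possible. It does not remove the point, because the protocol chose a mandatory rule for these four states and then limited it in time. After the cutoff, discretion is all that remains.

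Two further objections also stand in part. Only fMRI as session 3 is explicit, and in 2 of 6 orders the drug session is second and so is covered; in those orders, however, the stress test is not. Extending the rule would also probably remove subjects mainly from the two depressed groups. That direction is plausible, but its size cannot be worked out from the documents.

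**Conclusion.** The concern holds. The withdrawal rule has the wrong scope: it ends at session two of four, and under either reading of the second session it leaves out the drug session, the stress test or both. The gap is confined to mandatory withdrawal; monitoring, physician evaluation and emergency care continue.

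The conclusion rests on the text as written, with PET as session 4 and ERP as session 2 inferred under the numbered reading. The calendar-order result needs neither inference. The number of subjects affected cannot be estimated, since the documents give no event rate and no frequencies of session order. It is probably small, not least because the Randomization text in Section V.a expects at most a few final participants. Estimates, tests and power are unaffected. This should be corrected as a matter of subject safety; it does not threaten the study's results.

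**What to change.** In Section IV.a, end the withdrawal window at the conclusion of the subject's final study session, including any skin biopsy. In Section VII.d, add one sentence: a subject who becomes suicidal, homicidal, manic or psychotic at any session is withdrawn, in addition to the emergency handling already described there.

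Because the word suicidal is not defined in the rule, while the entry criterion leaves the threshold to the study clinician, the same amendment could usefully say who makes the call. The suicidality scale is specified only at the SCID and fMRI sessions, so at the ERP and PET sessions the extended rule would rely on observation unless the scale is added there.

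The cost is one phrase and one sentence in a minor amendment, and possibly a few more withdrawals with loss of their later-session data. Any such withdrawals should be reported by group. The analysis methods do not change.

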Specific Aim 3: To investigate stress sensitization of the mesocortical system following CSA. We will use high-density, source localized electrophysiology (EEG), and cortisol assessments to probe cortical activation and stress reactivity during a reward learning paradigm performed under acute stress. Relative to control and CSA/RES subjects, the CSA/MDD group will show decreased ventromedial prefrontal cortex (vmPFC) activation and increased cortisol reactivity following acute stress accompanied by impaired reward learning (**Hypothesis 3a**). Relative to healthy controls, the CSA/RES

group will show increased vmPFC activation but similar reward sensitivity and cortisol reactivity (**Hypothesis 3b**).

Specific Aim 4a: To investigate DAT function from DA neurons derived from directed conversion of skin fibroblasts. We will collect a skin biopsy from a subset of the study sample (20 participants) to analyze human-induced neuronal DA cells. We hypothesize that relative to the healthy group (n = 8), individuals with MDD and a history of CSA (n=8) will show altered/downregulated DA-related phenotype (e.g., DAT downregulation; **Hypothesis 4a**). **Similarly, we hypothesize that the CSA/RES subjects (n=4) will show similar DA-related phenotype as the healthy group.**

Specific Aim 4b: To Investigate relations between DAT function and fMRI, PET, ERP, endocrinological and behavioral markers of anhedonic behavior and stress responsiveness. Across all groups, downregulated DAT function will be associated with decreased ¹¹C altropane binding in striatal regions (PET), lower reward-related striatal responsiveness (fMRI), potentiated stress-induced cortisol responses, and stress-induced anhedonia (**Hypothesis 4b**).

Specific Aim 4c: To provide more conclusive tests of the potential role of DAT and NOC dysfunction in the pathophysiology of depression. Post-mortem tissue will be obtained from the Douglas Bell Canada Brain Bank in Montreal, QC, Canada through our collaborator [name], Professor and Chair, Department of Psychiatry, McGill University. Please see Appendix 2 for more details.

III. SUBJECT SELECTION

Inclusion Criteria:

- Females of all ethnic origins, age between 20 and 45; right-handed (Chapman & Chapman 1987);
- Absence of any psychotropic medications for at least 2 weeks (6 weeks for fluoxetine; 6 months for neuroleptics; 2 weeks for benzodiazepines; 2 weeks for any other antidepressants);

Childhood Sexual Abuse/MDD (CSA/MDD):

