A subset of subjects (20 participants) will be invited to participate in an additional study component involving a skin biopsy (see details below) after they have completed the ERP session. A subset of participants from the healthy group (n=8), CSA/MDD group (n=8), and the CSA/RES group (n=4) will participate. Invitations to participate will be extended to all subjects in the healthy group, CSA/MDD group, and CSA/RES group until recruitment for this additional component is complete. Participation in the additional session will require signing of a separate consent form prior to participation. In order to minimize phenotypic heterogeneity and maximize our ability to detect group differences, we will prioritize the cell conversion for participants based on their performance in a laboratory-based measure of anhedonia, the Probabilistic Reward Task (PRT), administered during the ERP session. Specifically, we will prioritize the subjects in the CSA/MDD group showing the greatest impairments in reward learning (as assessed by the PRT) when tested under stress and the healthy control subjects showing the greatest resistance against stress-induced reduction in reward learning (as assessed by the PRT). For all other subjects that do not meet this criteria (including all subjects in the CSA/RES group), skin samples will be frozen until additional funding is acquired. If any of these subjects refuse to participate, investigators will continue prioritizing subjects showing the next greatest level of impairment or resistance (as assessed by the PRT) until they find 3 subjects in each group. A normative database collected by [name] laboratory will be used to identify participants meeting pre-specified cutoffs with respect to their performance in the PRT during stress.

b. Procedures for obtaining informed consent

After screening and approval for participation, subjects will read and sign an IRB-approved informed consent detailing the general purposes and procedures of the experiment, and any questions they may have will be answered. The subjects of this study must be judged capable of understanding the nature of this study as well as the discomforts and potential benefits. This determination will be made by a

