Comparison of Molecular and Cellular Properties of Converted DA Neurons from Fibroblasts of MDD/CSA (n=8), CSA/RES (n=4), and Psychiatrically Healthy Subjects (n=8): Once we optimize conversion of fibroblasts to mDA neurons, we will use these biopsied fibroblasts to convert them to mDA neurons using our optimized protocol. To evaluate whether converted DA neurons from each group have distinct properties, we will test their ability to synthesize and release DA in response to membrane depolarization. We will treat *in vitro* differentiated cells with 50 mM KCl for 30 minutes and assess DA release by HPLC. Media will be collected after 30 min then concentrated perchloric acid (PCA) will be added to a final concentration of 0.1 M PCA/0.1mM EDTA. The DA content of the supernatants will be measured by reverse-phase HPLC. We will also compare mRNA expression patterns for dopamine-related genes such as synthesizing (TH and AADC), uptake (DAT), degrading (MAO and COMT), and storage function (VMAT2) at mRNA and protein levels in converted mDA neurons of each group.

Plasma Samples

Concentrations of pro- and anti-inflammatory cytokines and related receptors will be assessed using enzyme-linked immunosorbent assays (ELISA, R&D systems, Minneapolis, MN). All assays will be performed at the CLIA-certified Harvard Catalyst Central Laboratory (HCCL) in accordance with manufacturer specifications, and will be run in duplicate.

b. Study endpoints

Not applicable

c. Statistical methods

Please see above.

d. Power analysis

Sample size and power calculations

Sample size was estimated after considering effect sizes obtained in preliminary studies. Effect sizes were calculated using $p = 0.05$ for detecting differences between (1) controls vs. CSA/MDD, and (2) CSA/MDD receiving a DA challenge vs. placebo. Based on these estimates and allowing for 5% data loss, the sample size is 92 (23 subjects/group). In our study using the PSST task proposed, relative to controls, women with histories of CSA and MDD showed lower accuracy in trials in which they needed to rely on reward (Cohen's $d = -0.85$). In a study using the probabilistic reward task, we found that unmedicated MDD subjects had significantly reduced response bias compared to controls ($d = -0.70$; [name] et al 2009b). In another study using the same task, we found that healthy subjects receiving

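### Aim 4a is stated as an 8/8/4 comparison, but the first round converts about 3 CSA/MDD and 3 control samples from opposite ends of PRT performance and defers the rest, so a first-phase difference cannot be attributed to group

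*Combined protocol and SAP*

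**What the plan says.** **Hypothesis (II, Specific Aim 4a).** The expected difference is worded by group: "relative to the healthy group (n = 8), individuals with MDD and a history of CSA (n=8) will show altered/downregulated DA-related phenotype". A second part expects no difference: "the CSA/RES subjects (n=4) will show similar DA-related phenotype as the healthy group".

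**Analysis (VI.a, Skin Fibroblast Analyses).** The comparison of converted neurons is headed with the same sizes: "Fibroblasts of MDD/CSA (n=8), CSA/RES (n=4), and Psychiatrically Healthy Subjects (n=8". It names no statistical test and mentions neither selection nor a funding condition.

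**Enrollment (IV.a).** The biopsy numbers agree: "A subset of participants from the healthy group (n=8), CSA/MDD group (n=8), and the CSA/RES group (n=4) will participate". Conversion is a separate step. Investigators will "prioritize the subjects in the CSA/MDD group showing the greatest impairments in reward learning" under stress, and among controls those whose reward learning is most resistant to stress. The stated purpose is to reduce heterogeneity and make group differences easier to detect. If someone refuses, the search continues down the list "until they find 3 subjects in each group". For everyone else the text reads "including all subjects in the CSA/RES group), skin samples will be frozen until additional funding is acquired". Cutoffs from a normative database are mentioned but not given.

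**Procedures (V.a, Skin Fibroblast Component).** Biopsy is by willingness and conversion is prioritised by PRT performance. This agrees with IV.a.

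**Specific Aim 4b.** Lower DAT function is expected to go with stress-induced anhedonia, among other markers.

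**The concern.** Two things do not fit together.

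The first is the numbers. A reader of Aim 4a and the analysis section expects 8, 4 and 8 converted samples. A reader of IV.a expects about 3, 0 and 3 until more money is found. Nothing in the aim or the analysis section warns of this.

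The second is attribution. The two groups are picked from opposite ends of reward learning. Any cell marker that correlates with that measure will then differ between the selected subjects, even if the groups as a whole do not differ. The plan itself expects such a correlation: Aim 4b links DAT function to stress-induced anhedonia, and IV.a describes the PRT as a laboratory measure of anhedonia. If Aim 4b is right, a first-phase difference under Aim 4a has a ready explanation other than CSA/MDD status. The analysis section has no step that separates the two.

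**Working it through.** **1. The plan's own figure.** 8 + 8 + 4 = 20, which matches the stated subset of 20. The documents give no effect size, power or sample-size calculation for Aim 4.

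**2. The places side by side.**

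| Place | CSA/MDD | CSA/RES | Healthy | PRT selection | Funding condition |
|---|---|---|---|---|---|
| II, Aim 4a | 8 | 4 | 8 | no | no |
| VI.a, analysis | 8 | 4 | 8 | no | no |
| IV.a, biopsied | 8 | 4 | 8 | no | no |
| IV.a, converted first | 3 | 0 | 3 | yes, opposite ends | rest deferred |

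**3. Expected gap from selection alone.** Assumptions, none of them from the documents: one standard normal PRT score per subject; identical score and marker distributions in both groups; marker-PRT correlation r; the lowest 3 of 8 taken in CSA/MDD and the highest 3 of 8 in controls; no cutoffs. The pool is 8 because that is the number biopsied per group.

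The expected three largest of 8 standard normal values are 1.424, 0.852 and 0.473.

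Mean = (1.424 + 0.852 + 0.473) / 3 = 0.916.

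Expected gap in the marker = 2 × r × 0.916 SD:

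- r = 0: 0
- r = 0.1: 0.18 SD
- r = 0.3: 0.55 SD
- r = 0.5: 0.92 SD

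**4. False-positive rate.** This is the rejection rate of a two-sided 5% two-sample t-test, 3 against 3, simulated under the same assumptions with no true group difference.

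| r | Opposite tails, 3 of 8 |
|---|---|
| 0 | about 5% |
| 0.1 | 5.4% |
| 0.3 | 8.7% |
| 0.5 | 16% |

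Three subjects drawn at random, or all 8 per group, stay at about 5% whatever r is. The excess therefore comes from the selection rule and not from the small numbers.

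**5. Effect on Aim 4b.** In the 6 selected subjects, a true marker-PRT correlation of 0.30 appears on average as about 0.32. At this pool size the inflation is small.

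**6. What the sizes could show, if a t-test were used.** The effect detectable with 80% power is 1.51 SD at 8 against 8, and 3.07 SD at 3 against 3. For CSA/RES against healthy with every sample converted, the 95% interval half-width is 2.228 × √(1/8 + 1/4) = 1.36 SD (10 degrees of freedom). Even the full 4 against 8 would say little about similarity, and no equivalence margin is given.

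**The case against.** The strongest reply is that IV.a sets an order and not a limit. It speaks of priority, and the remaining samples are kept and not discarded. On that reading 8/8/4 is the full plan and the first 6 are where conversion starts. The figure of 3 appears in a sentence about refusals, so it is a first-round target and not a cap on the analysis. This stands. A reader might infer that Aim 4a is limited for good to 3 per group, or that its CSA/RES half cannot be tested at all. The documents support neither: both hold only if no further funding is obtained.

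The enrichment is also stated openly, with its reason, in a small laboratory component whose conversion method is still being optimised. That is a legitimate design. Disclosure in IV.a does not carry over to Aim 4a or the analysis section, however, and both still word the inference as CSA/MDD against healthy.

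The model in the working is simplified. IV.a ranks CSA/MDD subjects on impairment under stress and controls on resistance to a stress-induced decline, which read as two related measures and not one score. The cutoffs are not given either. The gaps are therefore illustrative. It would also be tempting to work out the bias for 3 chosen from all 23 per group, which gives larger figures, but only 8 per group are biopsied, and those by willingness.

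On Aim 4b, PET binding, fMRI response and cortisol are not the selection variable, so the objection to the PRT-based correlation does not extend directly to them.

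**Conclusion.** The concern holds as a mismatch of wording and inference. Aim 4a and the analysis section should not present an 8/8/4 group comparison without the conversion rule in IV.a. In the first phase, a CSA/MDD versus control difference cannot be attributed to group. The selection alone could produce a gap from 0 to about 0.9 SD, and a false-positive rate from 5% to about 16%, for an assumed correlation from 0 to 0.5. If the correlation is zero there is no bias, but Aim 4b predicts that it is not zero. That the correlation exists is the plan's own hypothesis; its size, the single score and the t-test are assumptions made here.

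The CSA/RES part of Aim 4a has no converted samples in the first phase, and whether it is ever tested depends on funding. The randomised amisulpride comparison is not affected.

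**What to change.** - Make Specific Aim 4a, section IV.a and the Skin Fibroblast Analyses agree on two sets of numbers: converted now (3 CSA/MDD, 3 controls, 0 CSA/RES) and conditional on funding (up to 8/8/4).
- State that the first-phase contrast is a descriptive comparison of PRT-selected extremes. Reserve the CSA/MDD versus healthy test of Aim 4a for when all biopsied samples have been converted.
- State that the CSA/RES part of Aim 4a is not tested unless funding is obtained.
- In the selected sample, do not read the Aim 4b correlation with PRT-based stress-induced anhedonia as a population estimate. The PET, fMRI and cortisol parts can stay, labelled exploratory.

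The sponsor could instead draw the first samples at random within group, or by one PRT rule applied in the same direction to both groups. Either would keep the group attribution but give up some phenotypic contrast. This is an option and not a required change.

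The cost is protocol wording and a weaker first-phase claim. No extra participants or biopsies are needed.
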